4.1. General Considerations

All baseline variables will be reported using the appropriate statistics: categorical variables by frequency tables (frequencies and percentages) and continuous variables by sample statistics (i.e., mean, standard deviation, minimum, median, quartiles, and maximum). The number of participants screened will be summarized for both the lead-in and randomized cohorts.

The efficacy related endpoints will be evaluated in the evaluable population while the safety endpoints will be evaluated in the safety population.

Efficacy endpoints will consider data until last dose of study drug (while on treatment).

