The conduct of the randomized phase is binding to a condition of obtaining an estimated mean percent increase from baseline in serum testosterone level at 12 weeks of less than 45%, and non-binding to a condition that the incidence of feminizing side effects observed is below that previously reported (CC)

The Sponsor reserves the right to conduct or stop the lead-in phase in case data on testosterone levels from patients treated with darolutamide alone would become available from other ongoing studies.

Page: 20 of 86

1.4.1.2 Randomized phase:

A maximum of 40 participants (20 per arm) will be randomly assigned to study treatment (darolutamide or enzalutamide) such that approximately 34 evaluable participants complete the study. The randomized stage will require a sample size of 20 per group to provide 85% power to test the null hypothesis of no-difference between groups on mean percent change at two-sided 0.05 level. This assessment is based on a mean percent change in serum testosterone from baseline and Standard Deviation for the darolutamide arm of 45% and 65% versus 110% and 75% respectively for enzalutamide. The final sample size and time of testosterone assessments may be modified according to the results of the lead-in phase.

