^h Tests related to inclusion exclusion criteria should be performed at screening visit. Neutrophil count, Platelet count, Total bilirubin, ALT, AST, Creatinine, Creatinine clearance, PTT, PT, INR. All the other clinical chemistry and hematology are mentioned in Section 10.2, Table 10-1.

¹ PROMIS, Self-Efficacy Assessment, and GODIN survey are not mandatory if translated version in not available. Questionnaires required are detailed in Section 10.4.

Assessment to be done in triplicate.

Page: 25 of 86

Table 1-5: Schedule of Activities Active Follow-up period

CTUDY ELEMENT/DEDIOD	Fau Dationto	ACTIVE FOLLOW UP PERIOD For Patients who discontinue treatment REFORE completing week 52 treatment for both Lead-in and Randomizer										
STUDY ELEMENT/PERIOD	For Patients who discontinue treatment BEFORE completing week 52 treatment for both Lead-in and Randomized Phases: Weeks											
VISIT (acceptable time window: days)	2 [± 7 d]	4 [± 7 d]	8 [± 7 d]	12 [± 7 d]	16 [± 7 d]	24 [± 7 d]	36 [± 7 d]	52 [± 7 d]				
Fasting glucose, fasting insulin, hemoglobin A1C, lipid profile, lean body mass ^a , fat mass ^a , weight		х		х		х	х	х				
Clinical chemistry (liver), hematology ^e		х		х		х	х	Х				
DHT, DHEA, SHBG, androstenedione, prolactin, estradiol		х		х		х	х	Х				
Vital signs		x		x		X	x	X				
Bone specific alkaline phosphatase (BSAP) and CTX		х		х		х	х	Х				
Efficacy												
Testosterone, free testosterone	Х	х	X	X	X	X	X	X				
Serum PSA	Х	х	X	x	x	X	x	X				
Gonadotropins, LH, FSH	х	х	Х	х	х	Х	х	Х				
24 DEXA scan								Х				
Patient reported outcomes												
FACT-P		х		х		Х	х	Х				
Surveys: physical function ^b				х		Х		Х				
Safety												
AE/SAE assessment ^c					Xd							

^a Bioelectrical impedance scale to be used.

Bayer will provide questionnaires wherever validated version is available in the said language.

Abbreviations: A1C (hemoglobin) Glycated, AE adverse event, ALT Alanine aminotransferase, AST Aspartate aminotransferase, BSAP bone-specific alkaline phosphatase, CT computerized tomography, CTX C-telopeptide, DEXA dual energy x-ray absorptiometry, DHEA dehydroepiandrosterone, DHT dihydrotestosterone, FACT-P Functional Assessment of Cancer Therapy – Prostate Cancer, FSH follicle-stimulating hormone, INR international normalized ratio, LH-luteinizing hormone, PSA Prostate-specific antigen, PT prothrombin time, PTT partial thromboplastin time, SAE serious adverse event, SHBG sex hormone-binding globulin.

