6.8 Treatment After the End of the Study

After completion of the last visit in Treatment period (evaluation at 52 weeks), all participants will be offered to continue with the treatment of darolutamide as long as they derived benefit, at the discretion of the investigator. All patients having been randomized to enzalutamide will be given the option to discontinue enzalutamide or offered to switch to treatment with darolutamide in this period.

For safety assessments, please refer to Section 8.7. The Sponsor reserves the right to terminate access to study intervention, in particular if the study is terminated due to safety concerns.

7. Discontinuation/Withdrawal Criteria

All participants who enter the study should complete all applicable study periods. Participants can be withdrawn from any study period at any time. Discontinuation of study treatment alone does not constitute withdrawal from the study.

Participants who discontinue the study treatment for any reason are to remain on the study for follow-up of primary, secondary and other objectives until week 52 (e.g., continue in the active follow-up periods, Table 1–5). Participants are expected to participate in active follow-up unless they explicitly object. Withdrawal of consent to the study treatment should be documented in the participant's medical record. If the participant does not wish to be followed up further, this additional consent withdrawal for follow-up must also be documented.

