9.4 Statistical Analyses

This section is a summary of the planned statistical analyses of the primary and secondary endpoints. Additional exploratory analyses of the data will be conducted as deemed appropriate.

All baseline variables will be reported using the appropriate statistics: categorical variables by frequency tables (frequencies and percentages) and continuous variables by sample statistics (i.e., mean, standard deviation, minimum, median, quartiles, and maximum). The number of patients screened will be summarized for both the lead-in and randomized cohorts.

The primary analysis for the lead-in phase of the study will occur when the last participant has been on the treatment for at least 12 weeks, unless the participant discontinued due to lost to follow-up, withdrawal, or death. The primary analysis for the randomized phase will occur when all the patients in the randomized phase have been on the treatment for at least 12 weeks. Final analysis for both phases of the study will occur when the last participant on randomized phase has been on the treatment for at least 52 weeks after the start of study intervention, unless the participant discontinued due to lost to follow-up, withdrawal, or death. Separate analyses will be performed for the lead-in phase and the randomized phase of the study.

The statistical analysis plan (SAP) will be developed and finalized before database lock and will describe the participant populations to be included in the analyses and procedures for accounting for missing, unused, and spurious data.

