ARAMON is designed to evaluate the efficacy and safety of treatment of men with hormone sensitive prostate cancer experiencing biochemical recurrence (BCR) with darolutamide or enzalutamide monotherapy. Efficacy outcomes measured will include serum testosterone levels, PSA levels and hormonal changes derived from the androgen axis including endocrine and energy metabolism markers and changes in bone mineral density. Study will also evaluate safety and quality of life, as well as fitness and physical function.

The analysis of the study will be conducted at three data cuts expected after about 12 weeks after start of darolutamide therapy for the lead-in phase, after 12 weeks post-randomization in the randomized phase and at end of the randomized phase. Table, figure and listing specifications are contained in a separate document.

Currently, there are no changes to the analyses described in the protocol amendment 1.0.

ARAMON V3.0 Page: 7 of 31

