4.5.1 Extent of Exposure

Study drug is defined as darolutamide for the lead-in, and darolutamide and enzalutamide for the randomized phase. As a rule, trailing "0 mg" records, which are not followed by any positive amount of drug, will not be included in the calculation of any drug duration or amount. Similarly, trailing "drug interruptions" will not be used in statistical tables. Interruption becoming permanent study treatment discontinuation is not accounted as an interruption.

Descriptive statistical summaries will be provided for the for the following variables:

• Overall time under treatment (or treatment duration)

Including time off drug and dose interruptions. It will be calculated in days and presented in months as (date of the last dose of any study treatment – date of the first dose of any study treatment + 1) / 30.44.

Actual dose per day

Actual dose per day = total amount of dose / number of days with intake > 0

• Total amount of dose

Total amount of dose = sum of dose received over total time under treatment

• Percent of planned dose received.

Percent of planned dose received = total amount of dose [mg] / planned dose [mg] * 100%; planned dose is sum of the intended initial dose according to protocol over total time under treatment.

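### A week-12 testosterone value decides who enters the PSA, hormone, metabolic and FACT-P analyses, so patients with usable data of their own are dropped; one PSA summary also departs from the SAP's on-treatment rule

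*SAP*

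**What the plan says.** **Who is analysed.** Protocol 9.3 (Tables 9-1 and 9-2) and SAP Section 3 (Tables 3-1 and 3-2) call a patient evaluable if he met the eligibility criteria and has testosterone at both baseline and week 12. Protocol 9.4.2 puts every secondary endpoint except AEs in this set. SAP 4.1 puts efficacy-related endpoints there, and SAP 4.3 all secondary endpoints except safety ones. SAP 4.3.1.1 divides PSA responders by the number evaluable.

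**Which values count.** SAP 4.1 sets a general rule: "Efficacy endpoints will consider data until last dose of study drug (while on treatment". Testosterone falls under it, since SAP Section 1 says "Efficacy outcomes measured will include serum testosterone levels, PSA levels and hormonal changes". SAP 4.1.2 adds that, except as noted, missing data are neither estimated nor carried forward. SAP 4.3.1.1 nevertheless ends its PSA definitions with a summary of maximum decline over all time on study.

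**What is collected.** Under Protocol Section 7, patients who stop treatment "are to remain on the study for follow-up of primary, secondary and other objectives until week 52". Protocol "Table 1-5: Schedule of Activities Active Follow-up period" includes testosterone and PSA at week 12.

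**What is declared.** Protocol 9.4 says that the SAP "will describe the participant populations to be included in the analyses and procedures for accounting for missing, unused, and spurious data". SAP Section 1 states "Currently, there are no changes to the analyses described in the protocol amendment 1.0", and SAP 4.8 likewise reports none.

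**What hangs on the primary estimate.** Protocol 1.4.1.1 makes the randomized phase conditional on "obtaining an estimated mean percent increase from baseline in serum testosterone level at 12 weeks of less than 45" percent.

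**The concern.** The week-12 testosterone sample is needed for the primary endpoint. It is not needed to compute a patient's PSA response at week 4, his lipids, his estradiol or his FACT-P score. Making it an entry condition for those analyses discards observed data. It also makes the results describe only men who reached a week-12 draw. In the randomized phase that condition is met or failed after randomization, possibly for reasons linked to treatment, so the arms compared need no longer be the arms randomized.

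The smaller matter is consistency. One PSA summary is worded to take in values after the last dose, which SAP 4.1 excludes. The plan also does not show how the lead-in estimate would look if the off-treatment week-12 values that the protocol collects were included, although that estimate is read against a binding 45% condition.

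**Working it through.** **1. Two patients traced through the plan**

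- *Patient 1* has baseline, week-4 and week-8 PSA and week-4 lipids, hormones and FACT-P, but no week-12 testosterone. SAP 4.3.1.1 requires confirmation 3 or more weeks later. Week 8 is nominally 4 weeks after week 4, so his week-4 PSA response can be confirmed. He is excluded from every one of these analyses, the week-4 results included.
- *Patient 2* stays on treatment to week 52 and misses only the week-12 draw. He is also excluded, even from the testosterone model for weeks 24 and 52.

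The mixed models in SAP Appendices 5 and 6 take one row per patient and visit, so nothing in them requires a week-12 row.

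**2. The plan's allowance** (Protocol 1.4, 9.2; SAP Section 5)

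- Lead-in: 25 assigned, 20 evaluable; 5/25 = 20% loss.
- Randomized phase: 40 assigned, 34 evaluable; 6/40 = 15% loss, and 40 × 0.85 = 34 as stated.

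**3. Effect on a PSA response rate**

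Let N be the patients treated, E those evaluable and R the responders among N. If every excluded patient is a non-responder, the evaluable rate is R/E against R/N, a factor of N/E.

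| Case | Factor |
|---|---|
| Lead-in, 1 lost | 25/24 = 1.04 |
| Lead-in, all 5 lost | 25/20 = 1.25 |
| Randomized, 1 lost | 40/39 = 1.03 |
| Randomized, all 6 lost | 40/34 = 1.18 |
| Loss unrelated to response | 1.00 in expectation |
| Lead-in, 20 of 25 respond, 5 responders lost | (15/20)/(20/25) = 0.75/0.80 = 0.94 |

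The factors 1.25 and 1.18 are ceilings for the planned loss. They charge the whole allowance to the week-12 sample, although evaluability also requires eligibility. The 1.18 is for both arms together, or for each arm if the loss is equal (20/17); the documents give no split by arm.

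**4. Off-treatment week-12 values and the 45% condition (illustration only)**

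Assume 20 patients, of whom k are off treatment at week 12. Let x be the geometric mean rise on treatment and r the fraction of the log rise lost after stopping. Neither k nor r is in the documents. The central value of the estimate with the k values included is

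100 × ((1 + x)^((20 − k·r)/20) − 1).

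| x | r | k = 1 | k = 2 | k = 3 |
|---|---|---|---|---|
| 50% | 1 | 47.0% | 44.0% | 41.1% |
| 50% | 0.5 | 48.5% | 47.0% | 45.5% |
| 40% | 1 | 37.7% | 35.4% | 33.1% |
| 30% | 1 | 28.3% | 26.6% | 25.0% |

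At x = 50% the result falls below 45% when k·r > 20 × (1 − ln 1.45/ln 1.50) = 20 × (1 − 0.3716/0.4055) ≈ 1.67. Full return is therefore not required: k = 3 with r = 0.6 gives k·r = 1.8, and k = 4 with r = 0.5 gives k·r = 2 and 44.0%. At 40% or 30% the estimate is below 45% with or without these values.

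**The case against.** **The evaluable set is a prespecified protocol choice.** The SAP follows it, PSA is compared descriptively, the lead-in has no hypothesis test, and the secondary significance flags are nominal. This stands. The point is not an SAP error and does not touch the primary comparison; it is an improvement available at low cost.

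**Scoring missing or unconfirmed PSA as non-response estimates something else.** Early leavers may have no confirming on-treatment value. This also stands, and is why the broader table belongs beside the evaluable table and does not replace it.

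**FACT-P may not be affected.** SAP 4.3 exempts safety endpoints, FACT-P shares an objective row with safety, and Protocol 8.7 lists it among safety assessments. Protocol 9.4.2 exempts AEs only, so the protocol's wording places FACT-P in the evaluable set. The SAP is less clear.

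**A reader might infer that SAP 4.1 contradicts the evaluable definition, or that an undeclared rule makes SAP 4.8 untrue.** The documents do not support either. The population tables say who is analysed; SAP 4.1 says which values count. A man who stops before week 12 and gives a later sample can be evaluable, contribute his on-treatment values and have no usable week-12 testosterone, which SAP 4.1.2 does not fill in. Protocol 9.4 leaves unused data to the SAP, and Protocol 1.4 itself speaks of patients treated for 12 weeks. The wording that does conflict is the PSA summary over all time on study.

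**Conclusion.** The main point holds. A week-12 testosterone value is an entry condition for PSA, sex-hormone and metabolic analyses and, on the protocol's wording, FACT-P, including week-4 results. In the randomized phase this is post-randomization selection. PSA response could be inflated by up to 1.25 (lead-in) or 1.18 (randomized phase, arms together), assuming the full allowance is lost through this requirement and only non-responders are lost. No inflation follows if loss is unrelated to response, and the rate would be understated if responders are lost, so 1.00 is not a lower bound.

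The on-treatment matter is minor: one phrase to align and one sensitivity estimate to add. A reader might infer that the lead-in decision is unsound as planned. It is not: SAP 4.1 already leaves off-treatment values out of the primary estimate. The illustration sizes only a sensitivity analysis, and its 50% case lies above the true rise assumed in Protocol 9.2.1 (below 45%). In that illustration the choice matters only for an on-treatment rise somewhat above 45% with several men off treatment and substantial return towards baseline.

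**What to change.** **Main change**

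- Fit the mixed models and FACT-P on eligible patients with a baseline and at least one on-treatment post-baseline value of the endpoint concerned.
- Keep the evaluable PSA table. Beside it, add one on all eligible treated patients (lead-in) or all eligible randomized and treated patients (randomized phase) with a baseline PSA. Count missing or unconfirmed as non-response, and treat values after the last dose as missing.
- State in the SAP which population FACT-P uses.
- Declare both population changes in SAP 4.8.

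**Minor change**

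- In SAP 4.3.1.1, limit the maximum PSA decline summary to on-treatment values.
- State that the primary estimate uses only week-12 values taken on or before the last dose, using the "date of the last dose of any study treatment" that SAP 4.5.1 already relies on.
- Report, beside the 45% condition, a sensitivity estimate that includes the off-treatment week-12 values collected under Protocol Table 1-5.
- Do not add an on-treatment condition to the evaluable definition. That would remove early stoppers with valid on-treatment PSA from the main PSA table and worsen the main problem.

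**Cost.** A few extra tables from data already scheduled, a declared departure from the protocol's analysis population, and possibly lower PSA response rates.

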10.2 Appendix 2: Clinical Laboratory Tests

- The tests detailed in Table 1–1 will be performed by the local laboratory.
- Protocol-specific requirements for inclusion or exclusion of participants are detailed in Section 5.1 and Section 5.2 of the protocol.
- Additional tests may be performed at any time during the study as determined necessary by the investigator or required by local regulations.

Page: 66 of 86

Table 10-1: Protocol-Required Safety Laboratory Assessments

Laboratory Assessments	Parameters		
Hematology	Hemoglobin Hematocrit RBC count	WBC Count with Differential: Neutrophils Lymphocytes Monocytes Eosinophils Basophils	Platelet Count
Clinical chemistry ¹	BUN or Urea	Potassium	Aspartate Aminotransferase (AST) / Serum Glutamic- Oxaloacetic Transaminase (SGOT)
	Creatinine	Sodium	Alanine Aminotransferase (ALT)/ Serum Glutamic- Pyruvic Transaminase (SGPT) Alkaline Phosphatase (ALP)
	Glucose (non-fasting) ²	Calcium (Total Calcium)	Total protein Total and direct bilirubin Albumin
Other screening tests	Testosterone PSA		

NOTES:

Abbreviations: BUN blood urea nitrogen, PSA prostate specific antigen, RBC red blood cells, WBC white blood cells.

Investigators must document their review of each laboratory safety report.

¹ Details of liver chemistry stopping criteria and required actions and follow-up assessments after liver stopping or monitoring event are given in Section 7.1 and Section 6. All events of ALT ≥3 × upper limit of normal (ULN) and bilirubin ≥2 × ULN (>35% direct bilirubin) or ALT ≥3 × ULN and international normalized ratio (INR) >1.5, if INR measured, may indicate severe liver injury (possible Hy's Law) and must be reported as an SAE (excluding studies of hepatic impairment or cirrhosis).

² In case of fasting glucose is required, Daro should be taken after blood drawn with food as recommended.

Page: 67 of 86

10.3 Appendix 3: Adverse Events: Definitions and Procedures for Recording, Evaluating, Follow-up, and Reporting

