		Section 4.1.3: Remove 'within +/- 7 days of scheduled date'	Account for baseline measures done outside the window		
		Section 4.1.3: Clarify the nearest measure prior to the study drug administration date will be used for baseline	To include the baseline measures recorded in the 'Unscheduled' visit CRF pages		
		Section 4.1.3: Revise the logic to choose the measurement for the analysis	Remove ambiguity around 'scheduled date' and to include 'unscheduled' pos baseline measurement incase scheduled visits do not exist		
		Section 4.2.1: Remove 'darolutamide' from the primary analysis timepoint for randomized phase	Align with protocol v2.0 that last participant could be on either arm in randomized phase		
		Section 4.3.1.1 Change 'absolute' PSA response to 'Undetectable' PSA response, and 50% and 90% 'relative' PSA response to PSA50, PSA90.	Align with terminologies commonly used in other literature		
		Section 4.3.1.1 Remove relative 30% PSA response (PSA30)	To focus on PSA50 and PSA90 since response rate in mHSPC is very high		
		Section 4.3.1.1 Add 0.2 ng/mL detection limit value to PSA response rates definitions	Clarify detection limit		
		Section 4.3.1.1 Add Breast enlargement, Breast	Summarize all AEs classified as feminizing side-effects		
		mass, Breast swelling in gynecomastia Section 4.3.1.1 Add analysis of AEs of special	Summarize common AEs associated		
		Section 4.3.1.2: Add 'and a Toeplitz covariance structure' to the SAS PROC MIXED details	with ARI treatment Align with protocol v2.0		

Page: 5 of 31

ARAMON V3.0

_	1		
		Section 4.5: Remove language related to	Laboratory measures are not graded in
		grading of laboratory measures	this study
		Section 4.5.2 Remove TEAEs with incidence of	Not meaningful with the sample size of
		at least 5% table	the study
		Section 4.5.2 Add drug related TEAEs; add a	Elaborate safety findings
		comprehensive list of safety tables planned	
		Section 4.6.1: Add free testosterone as	Explore the treatment effect of
		exploratory analysis for lead-in phase primary	darolutamide on free testosterone
		analysis	
		Section 4.6.1: Remove FACT-P and exploratory	Prioritizing the important endpoints for
		endpoints from lead-in primary analysis	decision making to go into the
			randomized phase
		Section 6.1.1: Add Discontinued from treatment	Align with clarification on active follow-
		along with the primary reason for discontinuation	up in protocol v2.0
		in place of participants continued after treatment	

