1.2.1.2 Treatment period

The treatment period is defined as the time from the administration of first dose of study treatment until 52 weeks or unacceptable toxicity, withdrawal of consent, investigator's decision to stop therapy for the participant, participant decision to stop therapy, sponsor's decision to terminate the study, or death.

End of treatment (EOT) visit takes place 30 days (+7 days) after the last dose.

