4.1.3 Data rules

In case of repeated measurements over multiple dates per time point,

- For baseline, the nearest visit (scheduled or unscheduled) to the start of the study drug administration will be used;
- For post-baseline measures, the scheduled visit will be used. Unscheduled visits will be used if there are no scheduled visits then the first unscheduled visit will be used.

If there are repeated measurements per time point on the same day (e.g., laboratory values, vital signs, etc.),

- For baseline, the latest measurement will be used;
- at any post baseline time point, the first measurement at the visit will be used.

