4.5.2 Adverse Events

Treatment-emergent AE (TEAE) is defined as any event arising or worsening after the first dose of study drug until 30 days after the last dose of study drug.

An overview of TEAEs will be summarized for the appropriate safety analysis set at the three data cuts. The following summaries will be done.

- Overview of TEAEs
- TEAEs by MedDRA ad worst CTCAE grade
- TEAEs by MedDRA ad worst CTCAE grade 3, 4 or 5
- TEAEs: number of subjects by primary SOC and PT
- TEAEs leading to permanent discontinuation of study drug: number of subjects by primary SOC and PT
- Number of subjects with TEAE by PT in decreasing order
- Drug-related TEAEs: number of subjects by primary SOC and PT

• Drug-related TEAEs leading to permanent discontinuation of study drug: number of subjects by primary SOC and PT

Page: 18 of 31

- Number of subjects with drug-related TEAE by PT in decreasing order
- SAEs: number of subjects by primary SOC and PT
- TESAEs: number of subjects by primary SOC and PT
- Drug-related TESAEs: number of subjects by primary SOC and PT
- TE non-SAEs (excluding TESAEs): number of subjects by primary SOC and PT

Additionally, feminizing side effects as described in Section 4.3, will be summarized by

- Overview of TEAEs of feminizing side effects
- Number of subjects with TEAEs of feminizing side effects by PT in decreasing order
- Treatment-emergent study drug-related adverse events of feminizing side effects by MedDRA SOC and PT and worst CTCAE grade
- Number of subjects with TEAEs of feminizing side effects leading to permanent discontinuation of study drug by PT in decreasing order
- Number of subjects with drug-related TEAEs of feminizing side effects by PT in decreasing order
- Number of subjects with drug-related TEAEs of feminizing side effects leading to permanent discontinuation of study drug by PT in decreasing order
- SAEs of feminizing side effects: number of subjects by primary SOC and PT
- TESAEs of feminizing side effects: number of subjects by primary SOC and PT
- Drug-related TESAEs of feminizing side effects: number of subjects by primary SOC and PT

AEs of special topics will be summarized by

• Number of subjects with special topics for adverse events

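### SAP 4.1 ends efficacy data at the last dose with no grace period, so on-schedule week-52 values from men who completed treatment, including the only post-baseline DEXA, can be dropped

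*SAP*

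**What the plan says.** SAP 4.1 sets the limit for every efficacy endpoint: "Efficacy endpoints will consider data until last dose of study drug (while on treatment". Nothing is added for samples taken shortly after dosing ends, and a sample on the day of the last dose is not addressed. For adverse events the SAP does write an allowance. SAP 4.5.2 defines treatment-emergent events as "any event arising or worsening after the first dose of study drug until 30 days after the last dose of study drug".

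On timing, SAP 1.2.1.2 says: "The treatment period is defined as the time from the administration of first dose of study treatment until 52 weeks" (or until an earlier stopping reason). Protocol Tables 1-3 and 1-4 give the week-52 visit a window of ±7 days, and Table 1-4 shows no dispensing at week 52. Protocol 8.2 ties hormone sampling to the fasting lipid panel, and a note to Protocol Table 10-1 says: "In case of fasting glucose is required, Daro should be taken after blood drawn with food as recommended".

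On what is measured, testosterone change at week 52 is a secondary endpoint in both phases. DEXA is scheduled only at baseline and week 52, under the efficacy rows of the schedule. SAP Section 1 counts among the efficacy outcomes "hormonal changes derived from the androgen axis including endocrine and energy metabolism markers and changes in bone mineral density".

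On what follows, Protocol 6.8 says that after the week-52 evaluation "all participants will be offered to continue with the treatment of darolutamide as long as they derived benefit", at the investigator's discretion. Men on enzalutamide may stop or switch.

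**The concern.** The cut-off date and the visit window do not fit together. A man can take all 52 weeks of treatment, attend within the permitted window, and still have his week-52 sample dated after his last dose. An on-treatment strategy does not require his exclusion, but the sentence as written produces it.

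No other rule restores the value. SAP 4.1.2 says missing data are not estimated or carried forward unless noted, and no exception covers this case. For testosterone and the other repeatedly sampled markers, the mixed model can still use the man's earlier visits. For DEXA there is no earlier post-baseline visit, so an excluded scan leaves him with no bone density change at all. Protocol 8.4 commits to comparing that change between arms.

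With about 34 evaluable men planned in the randomized phase, even a partial loss matters. There is also a question of who is left: if doses after week 52 count, inclusion could depend on the decision to continue and, on some readings, on the arm.

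**Working it through.** **The plan's own figure.** The documents give no figure for week-52 data lost to the cut. The nearest design figure is 85% power with 20 per arm at week 12 (Protocol 9.2.2, SAP 5). It also supplies a log-scale SD.

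- Fold changes 1.45 (SD 0.65) and 2.10 (SD 0.75); log SD = √ln(1 + CV²) gives 0.428 and 0.346, root mean square 0.389.
- With the stated means read as geometric, the difference is ln(2.10/1.45) = 0.370.
- 0.370 / (0.389 × √(2/20)) ≈ 3.01, less 1.96 ≈ 1.05, so power is 85.3% (83.4% by noncentral t). The figure reproduces on this reading.

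**Share of completers' week-52 values lost.** Inputs: 52 weeks = day 364, and the window is days 357 to 371, which is 15 days. Assumption: visit days are uniform over the window. A value is lost when its date falls after the last dose.

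| Last dose | Visit days lost | Loss with no grace period |
|---|---|---|
| Dosing runs through the visit day | none | 0% |
| Day 364 | 365–371 | 7/15 = 46.7% |
| Day 363 | 364–371 | 8/15 = 53.3% |

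For a last dose on day 364, a grace period of 1 day leaves 6/15 = 40.0% lost, 3 days leaves 4/15 = 26.7%, and 7 days leaves 0%.

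**Precision in the 47% case.** With equal loss in both arms and no borrowing from other visits, the interval widens by 1/√(8/15) = 1.37. From 17 per arm, about 17 × 8/15 ≈ 9 remain. With SD 0.389 assumed to hold at week 52, the 95% half-width of the log ratio and the corresponding multiplicative factor are:

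- 17 vs 17: 0.272, factor 1.31
- 17 vs 9: 0.331, factor 1.39
- 9 vs 9: 0.389, factor 1.48

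The ratio 0.389/0.272 = 1.43 slightly exceeds 1.37 because the t quantile grows as the sample shrinks. If only one arm loses values, the widening is √[(1/17 + 1/9)/(2/17)] = 1.20 before that adjustment.

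**Balance between arms.** Take the 46.7% loss among men whose last dose is day 364, and assume 80% in each arm take up darolutamide after week 52. Those whose later doses count keep their value, so the loss is (1 − 0.8) × 7/15 = 9.3%.

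| Reading of the last dose | Darolutamide | Enzalutamide |
|---|---|---|
| Assigned drug only, later doses count | 9.3% | 46.7% |
| Any study drug, later doses count | 9.3% | 9.3% |
| Doses after week 52 do not count | 46.7% | 46.7% |

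Only the first reading gives an imbalance against enzalutamide, and it needs two conditions that the SAP does not state.

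**The case against.** The best defence is that the loss may never occur. Protocol 6.8 treats the week-52 evaluation as the last visit of the treatment period, and continuation is offered only afterwards. A last dispensing at week 36 does not show that supply ends on day 364. If men dose through the visit day, nothing is lost. This stands, and it is why the range starts at 0%. It does not remove the problem, because the treatment period is defined to end at 52 weeks and no text requires dosing up to a late visit.

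It can also be said that SAP 4.1.3 already protects the visit: "For post-baseline measures, the scheduled visit will be used". That rule chooses among repeated measurements for a time point and says nothing about the last dose, so it does not override SAP 4.1.

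Three stronger readings are tempting but unsupported.

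- **Values are lost more often on enzalutamide.** SAP 4.5.1 defines study drug in the randomized phase as both drugs, and SAP 1.2.1.2 closes the treatment period at 52 weeks. Either can remove the asymmetry. The draw-before-dose note names only darolutamide, so an imbalance could even run the other way.
- **Nearly all completers could be lost because the last dose is the evening before a fasting visit.** An individual man could be lost this way, since no drug is dispensed at week 52. But the note tells men to take darolutamide after the draw, which points to a dose on the visit day. The documents do not support a figure near 100%.
- **FACT-P is lost too.** SAP Section 1 lists quality of life apart from the efficacy outcomes, and SAP Table 1-2 pairs FACT-P with safety. It is not clearly under the efficacy cut.

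Finally, 1.37 overstates the effect for testosterone, because the models in SAP Appendices 5 and 6 use all visits. It fits best where there is no other post-baseline value.

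**Conclusion.** The point holds as a defect in a stated rule. Followed literally, SAP 4.1 can discard on-schedule week-52 efficacy values from men who completed treatment, and for DEXA no other post-baseline value exists.

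The size is conditional: 0% if dosing runs through the visit day, 47% if dosing stops on day 364 with visits uniform over the window, and 53% if it stops on day 363. The 1.37-fold widening belongs only to the 47% case, with equal loss in both arms and no use of earlier visits. Imbalance between arms is possible, but its direction is open until the SAP says which drug and which doses define the last dose.

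The endpoints affected are secondary and exploratory. The week-12 primary comparison is untouched for men still on treatment at that visit. Whether an on-treatment limit is the right strategy for men who stop early is a separate matter; this point concerns only where the limit falls. The change should be made before the week-52 data are analysed.

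**What to change.** Replace the sentence in SAP 4.1 with wording to this effect:

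> On-treatment efficacy data are those collected up to 7 days after the last dose of the assigned drug within the 52-week treatment period. For participants who complete 52 weeks of treatment, the scheduled week-52 assessment within its ±7-day window, including DEXA, is always included, regardless of any treatment taken after week 52. Both rules apply identically in both arms.

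The 7 days match the protocol's own visit window and also settle same-day samples. Naming the assigned drug and the 52-week period closes the question of balance between arms. The SAP should also say what counts as completing 52 weeks, and whether FACT-P falls under the efficacy limit.

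The cost is a short SAP amendment, with no change to visits, procedures or treatment. The downside is that some values will come from men up to 7 days off drug, which may slightly blur an on-treatment estimate. A listing of days from last dose to the week-52 sample, by arm, would let readers judge this.
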